#### **INTERNAL PILOT**

The main trial will be preceded by an internal pilot study of 6 months duration. This will follow the same processes as the main trial, and all patients recruited to the pilot study will be included in the final analysis. The pilot will take place in 40 representative sites to confirm recruitment rates, protocol compliance and data collection, and will aim to recruit 420 patients representing 10% of the total study sample.(36) In particular, we will audit: (a) screening data; (b) recruitment; (c) reasons for exclusion; (d) protocol adherence, crossovers and fidelity to the intervention; (e) implementation of the training and protocol into practice, using screening logs, case report forms (CRFs) and virtual site visits. We will also review the assumptions on which the sample size calculation is based.

The recruitment rate during the pilot study is shown in the recruitment section.

	Red	Amber	Green			
RECRUITMENT						
% Threshold	<60%	60-99%	100%			
Sites recruited	<25	26-39	40			
Total number of participants recruited	<252	252-419	420			
COMPLIANCE/ADHERENCE (of those recruited)						
% Threshold	<75%	75-85%	86-100%			
Total number of participants compliant	<180	180-305	306-420			

Trial progression criteria will be:

Success criteria for recruitment will be (a) 100% recruitment: progress to main trial; (b) 60-99% recruitment: progress to main trial with review of screening log and protocol, adjustments to the protocol and research processes as required and explore the possibility of additional sites; (c) less than 60% recruitment: progression to main trial not anticipated.

Success criteria for protocol adherence and fidelity to the intervention: (a) 86-100% adherence: progress to main trial; (b) 75-85% adherence: progress to main trial with intensive efforts to improve adherence informed by learning from pilot sites; (c) < 75% adherence: progression to main trial not anticipated.

These criteria will be reviewed by the Data Monitoring and Ethics Committee (DMC) and the Trial Steering Committee (TSC) in association with the HTA secretariat.

On reaching the pre-defined success criteria, the internal pilot will run seamlessly into the main trial. The pilot study results will be reported in the HTA Monograph in accordance with the CONSORT guideline for pilot studies (37).

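### The pilot progression table's adherence counts contradict its own percentages: 306 compliant of 420 is green by count but, at 72.9%, red by percentage

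*Protocol*

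**What the plan says.** The progression criteria are in Protocol section 6.2.1, under Internal Pilot. The pilot "will aim to recruit 420 patients representing 10% of the total study sample". The table has a recruitment block and an adherence block.

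- **Recruitment.** The red/amber/green percentages are below 60%, 60-99% and 100%. The participant row reads "Total number of participants recruited <252 252-419 420". The sites row reads below 25, 26-39 and 40.
- **Adherence.** The block is headed "COMPLIANCE/ADHERENCE (of those recruited)". Its percentages are below 75%, 75-85% and 86-100%. Its count row reads "Total number of participants compliant <180 180-305 306-420".

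The text below the table repeats the adherence criteria in percentages only: "a) 86-100% adherence: progress to main trial; (b) 75-85% adherence: progress to main trial with intensive efforts to improve adherence", and then "c) < 75% adherence: progression to main trial not anticipated". The Data Monitoring Committee and the Trial Steering Committee review the criteria together with the HTA secretariat.

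**The concern.** The two adherence rows should be one rule expressed in two units. The green count band ends at 420, so the count row appears to be set for a fully recruited pilot. Yet 306 of 420 is below the 75% line that marks red.

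These are the pre-specified criteria for moving from the pilot to the main trial. The same adherence result can point to unqualified progression under one row and to no anticipated progression under the other. Adherence also bears on whether the main trial can answer its question: the primary analysis is by intention to treat, sections 2.9.2 and 6.2.1 both say that crossover reduces power, and the sample size in section 6.1 states no allowance for it.

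**Working it through.** **Inputs** (all from Protocol section 6.2.1, Internal Pilot): target 420; adherence measured among those recruited; percentage cut-offs 75% and 86%; count cut-offs 180 and 306; recruitment floor for amber 252; 40 sites.

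**Control on the same table.** The participant recruitment row reproduces: 0.60 × 420 = 252. So that count row follows from its percentages and the target of 420.

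**Adherence row at 420.** Count cut-off = percentage × number recruited.

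- Amber floor: 0.75 × 420 = 315. Printed: 180, and 180/420 = 42.9%.
- Green floor: 0.86 × 420 = 361.2, so 362. Printed: 306, and 306/420 = 72.9%.
- Top of printed amber: 305/420 = 72.6%.

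| Compliant of 420 | Percentage | By count | By percentage |
|---|---|---|---|
| 180-305 | 42.9-72.6 | amber | red |
| 306-314 | 72.9-74.8 | green | red |
| 315-361 | 75.0-86.0 | green | below 86% |
| 362-420 | 86.2-100 | green | green |

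**Does another denominator reconcile the row?** Solving backwards:

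- 180/0.75 = 240, which is below the table's own red limit of 252 for recruitment.
- 306/0.86 = 355.8; taking the top of amber instead, 306/0.85 = 360.

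No single number recruited gives both cut-offs.

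**Behaviour at other pilot sizes.**

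- 252 recruited: 0.75 × 252 = 189. A count of 180 is 71.4%, so 180-188 is amber by count and red by percentage.
- 252-305 recruited: green by count cannot be reached even with every participant compliant, because it needs 306.
- 355 or fewer recruited: 306 is at least 86% (306/355 = 86.2%).
- 408 recruited: 306/408 = 75.0% exactly. From 409 upward, 306 is red by percentage.

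The counts are therefore too lenient near target and, for green, too strict at low recruitment.

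**Sites row.** The bands run from below 25 to 26-39, so 25 sites has no category. Also 0.60 × 40 = 24, so 24 sites is amber by percentage and red by count.

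**What adherence at these levels could mean for power (illustration).** Take section 6.1's 2,095 per group, 8.5% against 11.5%, two-sided 5%. With d the difference and p̄ the mean of p1 and p2, power = Φ{[d√n − 1.96√(2p̄(1−p̄))] / √(p1(1−p1) + p2(1−p2))}. This gives 89.9%, reproducing the stated 90%. Now assume equal non-adherence in both arms and proportions centred on 10%.

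- At 72.9% adherence, if non-adherent patients contribute no difference: d = 0.03 × 0.729 = 0.0219, power about 65%.
- At 72.9%, if all non-adherent patients cross over: d = 0.03 × (2 × 0.729 − 1) = 0.0137, power about 32%.
- At 42.9%, the printed amber floor, with no difference among the non-adherent: d = 0.03 × 0.429 = 0.0129, power about 28%.

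The contradiction in the table does not depend on these figures.

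**The case against.** The strongest reply is that the percentages appear twice, in the table and in the text, while the counts appear only once. A committee shown 306 of 420 would also see 72.9% against a written 75% line and would probably follow the percentages. Red says only that progression is not anticipated, and the committees keep discretion. Section 6.2.1 also commits to examining loss of power around the observed crossover rates at the end of the pilot and at each 6-monthly analysis, so a weak adherence result would not pass unseen. Finally, the green-to-red reversal needs at least 409 recruited and covers only nine counts even at 420.

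Much of this is fair. It lowers the chance that the committees would be misled, and the size of the discrepancy does depend on the number recruited. But nothing in the protocol says that the percentages prevail. The reversal is narrow, but the amber-by-count, red-by-percentage zone is not: at 420 it holds 126 counts (180-305). The power review is a separate exercise and does not set the threshold.

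Two further cautions stand. How 180 and 306 arose is not documented, so denominators of 240 and 360 are conjecture. The bands 75-85% and 86-100% also leave values between 85% and 86% undefined. At 420 that is 358-361, and rounding to whole percentages would make 360 and 361 green.

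**Conclusion.** The concern holds. The adherence count row does not follow from the stated percentages at the target of 420, and no other single number recruited makes it do so. At 420, every count from 180 to 314 is placed at least one band too favourably against the 75% line, and 306-314 is placed two bands too favourably. Counts 315-361 are green by count without reaching 86%; whole-percentage rounding would remove only 360 and 361 from that group.

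This rests on reading adherence as a proportion of those recruited, as the table says. The sites row has a smaller fault of its own: a gap at 25 sites and a cut-off that does not match 60% of 40. Because these are thresholds in the pre-specified progression criteria, they must be corrected. The protocol does not show whether the pilot decision has already been taken. If it has, the pilot report should state which row was applied.

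**What to change.** Preferred: make the percentage of those actually recruited the only adherence criterion and delete the row "Total number of participants compliant". This works at any pilot size.

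Alternatively, keep counts but correct them for 420 recruited: red below 315, amber 315-361, green 362-420, with a note that they scale with the number recruited.

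Either way, state how values between 85% and 86% are classed; the corrected counts treat anything below 86% as amber. Set the sites row to red below 24, amber 24-39, green 40.

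The cost is a table correction by protocol amendment. It needs no patients, no new data and no change to the design.

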#### 6.2.2 Planned recruitment rate

Recruitment has been based on the COMPRESS study (personal correspondence), which was a feasibility study comparing "hands-on" chest compressions with an automated external compressions device during adult in-hospital cardiac arrest, carried out by one of the co-applicant team ([name]) at the Warwick CTU. The clinical population for AIRWAYS-3 is very similar to that included in the COMPRESS study. In COMPRESS, which was more challenging to recruit to than this trial and did not recruit 24/7, the number of eligible patients was 2.1 times those randomised. In relation to these figures, and our sample size calculation, it is expected that 14,000 patients will be screened during the trial, of which 8,400 are expected to be eligible for AIRWAYS-3 and of those 4,200 (50%) will be recruited.

#### 6.2.3.2 Primary outcome analysis

The mRS is a 7-point scale which measures the functional outcome of patients. The scaling is as follows: 0 - No symptoms; 1 - No significant disability - able to carry out all usual activities, despite some symptoms; 2 - Slight disability – able to look after own affairs without assistance, but unable to carry out all previous activities; 3 - Moderate disability - requires some help, but able to walk unassisted; 4 – Moderately severe disability - unable to attend to own bodily needs without assistance, and unable to walk unassisted; 5 - Severe disability - requires constant nursing care and attention, bedridden, incontinent; 6 – Dead

#### 6.2.3.3 Secondary outcome analysis

Outcome	Source of Data	Justification				

Initial ventilation success (visible chest rise and evidence of end tidal carbon dioxide on capnography)	App data entry following IHCA	Primary goal of advanced airway management is to deliver effective ventilation
Regurgitation (stomach contents visible in the mouth or nose) or aspiration (stomach contents visible below the vocal cords or inside a correctly placed tracheal tube or airway channel of a supraglottic airway device)	App data entry following IHCA	Different advanced airway management techniques may be associated with different risks of regurgitation and/or aspiration
Return of spontaneous circulation (ROSC) > 20 minutes	NCAA and/or data collection by research staff at participating sites	Short-term outcome following cardiac arrest
Critical care length of stay (number of days from randomisation	NCAA and/or data collection by research staff at participating sites, HES	Measure of health service use, Required for health economic analysis
Hospital length of stay (number of days from randomisation)	NCAA and/or data collection by research staff at participating sites, HES	Measure of health service use, Required for health economic analysis
Survival to hospital discharge, 3- months and 6-months	NCAA and/or data collection by research staff at participating sites, HES	Included in the cardiac arrest core outcome set
mRS score at 3-months and 6- months	Postal CRF/eCRF/CRF completed by telephone	Included in the cardiac arrest core outcome set; patient-centred outcome
Health-related quality of life (EQ- 5D-5L) at 3-months and 6-months	Postal CRF/eCRF/CRF completed by telephone	Included in the cardiac arrest core outcome set; required for health economic analysis; patient- centred outcome
In-hospital stay utilization and costs	HES	Required for health economic analysis
Additional unscheduled care and readmission (to 6 months)	HES	Required for health economic analysis
Adverse events/ serious adverse events	CRF (in-hospital patient notes)	All serious adverse events and adverse events that are related to the intervention will be reported, in line with Warwick CTU operating procedures.

#### 6.3 Subgroup analyses

Sub-group analyses will include the assessment of treatment allocation, shockable/non-shockable initial rhythm and the presumed cause of the cardiac arrest. This pre-specified exploratory subgroup

analysis will be analysed using interaction terms (treatment x sub-group) in the statistical models and reported using 95% confidence intervals, as the trial is not powered to identify interactions.

# 6.4 Interim analysis and criteria for the premature termination of the trial

The DMC and TSC will assess recruitment, the interim analyses in terms of the statistical monitoring, data completeness and integrity, compliance to the intervention (i.e. crossover) and deviations from protocol. Formal interim analyses will be planned to assess early stopping either for efficacy or harm during the main trial, whilst maintaining the type I error rate of 5%. The following stopping rules are recommended and will be discussed further with the DMC: when approximately 10% (early monitoring) and 50% (mid-way monitoring) of the total patient data are available. The O'Brien and Fleming boundaries will be used to assess the primary outcome at each of the formal interim analyses,(46) as these methods will preserve the overall type I error rate of 5% and account for the fraction of data available as well as the unequal spacing in the analyses.

### 6.5 Patient population

Patients can be enrolled sequentially by clinical members of the cardiac arrest response team on a 24/7 basis. Recruitment will be carefully monitored using screening logs based on hospital emergency cardiac arrest call logs and data returned routinely to the National Cardiac Arrest Audit (NCAA) to ensure as many eligible patients are randomised as possible.

The broad inclusion/exclusion criteria will ensure that the trial findings are generalizable to the UK inhospital adult cardiac arrest population. This will maximize the opportunity for IHCA patients to participate in this research. Children are excluded because: i) the aetiology of cardiac arrest in children is more commonly due to a respiratory pathology such that tracheal intubation is more frequently used in this group and there is unlikely to be equipoise to randomise to a supraglottic airway; ii) differences in anatomy increase the complexity of airway management in children; iii) functional assessment measures in children are different to those used in adults such that it would not be possible to combine outcomes across children and adult groups. Patients are excluded if they sustain a cardiac arrest outside hospital and are transferred to the hospital whilst cardiac arrest and resuscitation are ongoing. This is a different patient population to which other evidence and randomised trials apply (20,21). Similarly, individuals who are not hospital inpatients will more closely resemble out of hospital cardiac arrest patients. In pregnancy, and particularly later pregnancy, tracheal intubation is generally preferred due to the increased risk of regurgitation and aspiration and the potential need to generate higher airway pressures; this means that equipoise does not exist in this patient group. Patients already receiving advanced airway management are excluded since it would be clinically inappropriate to remove a functioning advanced airway device as a result of study enrolment. Patients with a functioning tracheostomy are rare and require a specialist approach to airway management that is outside the scope of this trial.

#### 6.6 Health Economic Evaluation

A prospectively planned economic evaluation will be conducted from an NHS and personal social services perspective using NICE Reference Case approach (47). Resource use will include intervention, hospital (ICU, HDU and ward days) and community costs (primary care and social care costs) in the 6 months following randomisation. Resources will be costed using national reference unit costs where available, reflated to current prices. A secondary societal perspective will additionally include time lost from work (paid/unpaid) and patient borne health costs (e.g. wheelchair by type, home adaptations, feeding aids, walking aids, home-help, support from relatives). Health-related quality of life (EQ-5D-5L) responses will be used to generate quality-adjusted life years (QALYs) using the valuations recommended by NICE and using the area-under-the curve (AUC) method.(48,49) Baseline

EQ-5D-5L values will be set to reflect the unconscious health state minimising potential bias in the QALY AUC calculation.(50,51) Within-trial analysis (to 6 months) using bivariate regression of costs and QALYs will inform a probabilistic assessment of incremental treatment cost-effectiveness. Missingness mechanisms will be explored and multiple imputation methods used where appropriate to avoid biases associated with complete case analysis (52-54). Within-trial findings, reflecting the outcomes and prognosis of patients at 6 months, will inform a lifetime decision-analytic model. Modelling will draw upon best available information from the literature to supplement the trial data. Parameter uncertainty in the decision-analytic model will be explored using probabilistic sensitivity analysis. Longer term costs and consequences will be discounted to present values at 3.5% per annum. Sensitivity analyses will be undertaken to explore uncertainty and to consider issues of generalisability of the study. Presentation of findings for the within-trial analysis and model will include incremental cost-effectiveness ratio planes, incremental net monetary benefit, cost-effectiveness acceptability curves and value of information.

# 7. TRIAL ORGANISATION AND OVERSIGHT

#### 7.1 Sponsor and governance arrangements

The trial will be sponsored by University Hospitals Bristol and Weston NHS Foundation Trust (UHBW), and co-sponsored by University of Warwick to support International Recruitment. UHBW has substantial experience of the oversight of NIHR-funded clinical trials in the NHS. All trial-related activity will be undertaken according to the principles set out in the Good Clinical Practice Guidance and in accordance with the UK Policy Framework for Health and Social Care Research.

The study will be performed subject to favourable opinion/ authorisation/permission or equivalent from all necessary regulatory and other bodies relevant to UK or international sites (as appropriate). This includes but is not limited to REC, HRA, NHS Trusts.

#### 7.2 Ethics approval

Ethics committee review of the trial protocol and documents essential to the trial will be carried out by a UK NHS research ethics committee, flagged for studies involving adults lacking capacity. The required ethical approval for the trial will be sought using the Integrated Research Application System (IRAS). HRA approval will be obtained before the study starts, and when all other approvals are in place. Before enrolling patients into the trial, each trial site must ensure that the local conduct of the trial has been reviewed by the relevant NHS Trust Research & Development (R&D) department.

Sites will not be permitted to enrol patients into the trial until written confirmation of the approval via the HRA is received by the AIRWAYS-3 trial team, based at WCTU. As the trial will recruit participants without prior consent in accordance with the Mental Capacity Act 2005, approval will also be sought from the Health Research Authority Confidentiality Advisory Group (CAG) to support the processing of confidential data without consent.

Annual reports will be submitted to the REC within 30 days of the anniversary date on which the favourable opinion was given, and annually until the trial is declared ended. The REC and HRA will be notified of any amendments, and once the trial concludes a final report will be provided in accordance with reporting requirements. In accordance with Warwick SOPs, the CI is responsible for making applications to the relevant authorities if an amendment to the research protocol or other study document or process is required. The CI may designate a member of staff to prepare the amendment submission but retains responsibility for any amendment application, however, the CI is no longer

required to sign the completed amendment tool but should be copied into any correspondence with the relevant sponsors' office. It is the sponsor's responsibility to assess whether an amendment is to be regarded as 'substantial' on a case-by-case basis and confirm their opinion with the CI or their delegate prior to any application being made. The sponsor is required to review and sign off the amendment tool prior to locking for submission. This will be returned to WCTU for submission and processing of the amendment. The WCTU study management team will ensure that an impact assessment is carried out on all key study documents (e.g. protocol, CRFs, data management plan, SAP, Risk Assessment and Monitoring Plan) to check if any associated documents require amending based on the proposed amendments to the study.

As part of the funding decision by the NIHR HTA, the trial has been reviewed by both the HTA board and independent individuals with clinical, methodological, and patient involvement expertise. It is a requirement to send to the NIHR any substantial protocol amendment documents for their approval prior to submission to the main REC.

# 7.3 Confidentiality Advisory Group (CAG) approval

An application will be made to CAG to process confidential patient information without individual patient consent. There are several elements that will need to be considered and carefully described in the CAG application:

#### 7.3.1 Access to a deceased person's data

The majority of patients enrolled in the trial will die before regaining capacity. It is clearly not feasible to obtain consent from a person who is deceased. The next of kin cannot give consent in this situation, unless they are the Legal Personal Representative or the person administering the estate. As a result, we will apply to CAG to process a defined data set for deceased persons for the minimum time required to complete data analysis, after which the data set will be anonymised and all confidential patient information will be destroyed. This is particularly important to ensure 100% ascertainment of the primary outcome and is one of CAG's "precedent set categories" which have been developed to enable a more timely review process.

